4.5 DISCONTINUATION OF THE CLINICAL STUDY

The entire trial will be stopped if:

- Life-threatening vaccination-related toxicity is observed in more than one patient, termination of the trial will be discussed among all collaborators and the trial sponsor.
- The vaccine and/or its application is considered too toxic to continue treatment prior to meeting the recruitment target.

If the trial is discontinued patients should be treated according to accepted medical practice.

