4.4 WITHDRAWAL CRITERIA

Patients who are removed from the study treatment due to adverse experiences (clinical or laboratory) will be treated and followed according to accepted medical practice. All pertinent information concerning the outcome of such treatment must be recorded in the CRF.

Patients who withdraw their consent from participating in the trial will be withdrawn from protocol procedures. Data that has been collected on these patients to this timepoint will be included in the analyses.

The discontinuation of study treatment will occur under the following circumstances

- Unacceptable toxicity
- Any patient who experiences a WHO CTC grade 3 adverse reaction (AR), possibly or likely to be related to vaccination will discontinue further vaccination.
- Severe local toxicity (CTC 3 or greater) at the site of injection, development of clinically relevant anti-DNA antibodies or rheumatoid factors, clinical or biochemical evidence of muscle destruction (CTC 3 or greater) or other unexpected toxicity will lead to termination of the vaccination of that patient.

- Unforeseen events: any event which in the judgement of the Investigator makes further treatment inadvisable
- SAE requiring discontinuation of treatment
- The patient withdraws consent where a patient is not evaluable, additional patients will be recruited to replace them (See Section 3.1)
- Serious violation of the study protocol (including persistent patient attendance failure and persistent non-compliance)
- Evidence of disease progression
- In patients with CML requirement to discontinue or change the dose of tyrosine kinase inhibitor therapy

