12 TRIAL MANAGEMENT

12.1 TRIAL MANAGEMENT GROUP (TMG) AND DATA MONITORING ETHICS COMMITTEE (DMEC)

TMG

Trial Management Group (TMG) is responsible for overseeing progress of the trial. The day-to-day management of the trial will be co-ordinated through the UoSCTU and oversight will be maintained by the Trial Steering Committee and the Data Monitoring and Ethics Committee.

Listings of AR, AE, SAE and SUSARs will be reviewed every 2 to 3 months jointly by the study team (Trial Management Group to include members of UoSCTU and the clinical and laboratory investigators).

DMEC

A DMEC will be convened on behalf of and with input from the Trial Management Group at regular intervals to review the safety listings and recruitment. AR frequency and type will be collected and presented to the Trial Management Group and the independent DMEC. It will then fall to the DMEC to decide whether there is sufficient reason to suspend or terminate the study.

Additionally the DMEC will evaluate on an ongoing basis whether there is any evidence that the vaccination might disadvantage patients in either cohort of the study and in this case might recommend discontinuation.

Life-threatening vaccination-related toxicity is observed in more than one patient, termination of the trial will be discussed among all collaborators and the trial sponsor.

Unplanned DMEC meetings will be called if required during the study.

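### Sections 4.5 and 12.1 leave it unclear whether vaccination is halted, or termination only discussed, after a second life-threatening vaccine toxicity

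*Protocol*

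**What the plan says.** Protocol section 4.5 (Discontinuation of the clinical study) introduces its list with "The entire trial will be stopped if". The first bullet reads "Life-threatening vaccination-related toxicity is observed in more than one patient, termination of the trial will be discussed among all collaborators and the trial sponsor". The second bullet covers a vaccine, or its method of delivery, judged too toxic to go on with before recruitment is complete. It has no consequence of its own, so the mandatory stop in the opening line applies to it.

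Protocol section 12.1, under its DMEC heading, repeats the first condition as a free-standing sentence with the same ending: "termination of the trial will be discussed among all collaborators and the trial sponsor". The line about stopping the entire trial is not repeated there. On safety data presented to the DMEC, the same section says "It will then fall to the DMEC to decide whether there is sufficient reason to suspend or terminate the study". It also asks the DMEC to keep under review whether vaccination might disadvantage patients in either cohort, and adds "Unplanned DMEC meetings will be called if required during the study".

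The rules in section 4.4 work patient by patient. Listed toxicities "will lead to termination of the vaccination of that patient", and the investigator may also stop a patient's treatment under "Unforeseen events: any event which in the judgement of the Investigator makes further treatment inadvisable".

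**The concern.** One trigger is given two consequences. The opening line of 4.5 makes stopping automatic, whereas the bullet beneath it and section 12.1 promise only a discussion. The two sections also name different parties: the collaborators and sponsor discuss, while the DMEC decides. Neither section says how the two steps connect, or that the second event must itself lead to a DMEC meeting.

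What is at stake is the period between the second event and the decision. A site that follows the opening line would halt. A site that follows the bullet or section 12.1 would find nothing there that stops the next scheduled dose for a patient who is well, or the enrolment of a new HLA A2 positive patient. Section 9.4 names Southampton, Exeter and Hammersmith, so different sites could act differently on the same event. A trial-level safety rule should not depend on which sentence the investigator happens to read.

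**Working it through.** The protocol has no figure to reproduce here. The check is a comparison of texts, followed by a small illustration.

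**Step 1: the trigger and its consequence.**

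- Section 4.5, opening line: the entire trial stops.
- Section 4.5, first bullet: termination is discussed by the collaborators and the sponsor.
- Section 12.1, repeated sentence: the same discussion, with no stop.
- Section 12.1, DMEC paragraph: the DMEC decides on suspension or termination.

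Two readings fit. Under stop-then-discuss, dosing ends at the second event and the discussion concerns whether the stop becomes permanent. Under discuss-only, the second event starts a conversation and dosing is not addressed. The opening line of 4.5 supports the first reading. The free-standing sentence in 12.1 supports the second. Nothing else in the protocol chooses between them.

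**Step 2: does another provision order an interim hold for unaffected patients?**

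- Sections 4.4, 5.4 and 7.1.8: stop or pause vaccination in the affected patient only.
- Sections 4.4 (unforeseen events), 11.2 and 11.4: leave it to the individual investigator or clinician to withhold or change treatment.
- Sections 8.3.3 and 8.3.4: life-threatening events are reported within 24 hours, authorities are told of a life-threatening SUSAR within 7 days, and all investigators are informed of SUSARs. These provisions pass on information but order no hold.
- Section 9.3: a 48-hour evaluation after the first vaccination of the first HLA A2 positive patient at each site, not linked to this trigger.
- Section 12.1: ongoing DMEC evaluation of both cohorts, and unplanned meetings if required. The DMEC can act for the whole trial, but this trigger is not said to require a meeting.
- Section 4.5, second bullet: a full stop, but only once someone has judged the vaccine too toxic.

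None of these orders an interim hold on this trigger, and none rules one out.

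**Step 3: illustration of size.** The protocol gives no time for the discussion or for an unplanned meeting. Seven days is assumed here. It is borrowed from the limit in 8.3.4 for notifying authorities and is not a decision deadline. Section 5.2 gives dosing intervals of 4 weeks (28 days) and then 3 months (taken as 91 days). With visits spread evenly, the share of patients with a vaccination due in the interval is interval length divided by dosing interval:

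- 4-weekly phase: 7/28 = 0.25, about 25%, or 2.5 vaccination visits per 10 patients.
- 3-monthly phase: 7/91 = 0.077, about 8%, or 0.8 vaccination visits per 10 patients.

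These are doses due, not doses given. They become exposure only if sites take the permissive reading and keep dosing.

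**The case against.** The strongest reply is that this is a drafting slip: a complete sentence was placed under an opening line it does not fit, and the stop-then-discuss reading removes the conflict. That reading is available, and section 12.1 itself distinguishes suspending from terminating. A reader might infer that the two consequences are flatly incompatible, but the text does not support that. The ambiguity nevertheless stands, because 12.1 states the discussion alone and a site working from that section would see no stop.

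A second reply is that the protocol protects unaffected patients by other routes. This is largely right. A reader might infer that nothing operates at trial level, and that would be wrong: there are the DMEC's continuing evaluation of both cohorts, its power to suspend or terminate, unplanned meetings, the second bullet of 4.5, 24-hour reporting and SUSAR notification to all investigators. These make prompt action likely. They do not say what happens to dosing in the meantime.

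A reader might also infer that dosing could continue for months, since the stated review frequency is "Listings of AR, AE, SAE and SUSARs will be reviewed every 2 to 3 months". The documents do not support this. That is the routine review of listings by the study team. A second life-threatening event would come to light sooner through expedited reporting, and an unplanned DMEC meeting could be called.

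Finally, the practical weight is modest. Section 1.9 reports no vaccine-related serious adverse events in more than 80 patients in the group's earlier studies, so the trigger is expected to be rare. That limits the importance of the point but does not answer it. The rule exists for the rare case, and the protocol has chosen to state it.

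**Conclusion.** The point holds as an inconsistency in a stated trial-level safety rule. After life-threatening vaccine toxicity in a second patient, the protocol can be read as requiring either a halt followed by discussion, or discussion alone. It does not settle whether unaffected patients may be vaccinated, or new vaccine-arm patients enrolled, before a decision is made. It does not amount to permission to keep dosing, and trial-level oversight is not absent.

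The textual finding rests on no numerical assumption. The figures of about 25% and about 8% rest on three: a 7-day interval, evenly spread visits, and sites that continue dosing. They show only the order of the possible exposure. No endpoint, sample size or analysis is affected. The correction is worth making because a safety rule should be capable of being followed in one way only, and the change is small.

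**What to change.** State one consequence for this trigger, in identical words, in sections 4.5 and 12.1. That alone cures the inconsistency.

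Recommended content: when life-threatening toxicity related to vaccination is seen in a second patient, further vaccination and new vaccine-arm enrolment are suspended in both cohorts and an unplanned DMEC meeting is called. The DMEC then decides, after hearing the collaborators and the sponsor, whether the trial resumes or terminates. This goes beyond the minimum correction. It is preferred because it keeps the existing trigger and the DMEC's existing role, gives the collaborators and sponsor a defined place, and settles dosing in the interval.

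The cost is one replaced sentence in each of two sections, by amendment. If the trigger is ever met, there is also a short interruption of dosing in both cohorts.

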5 TREATMENTS

HLA A2-ve patients will receive standard care in accordance with accepted medical practice.

HLA A2+ patients will receive the treatment described in Sections 5.1 to 5.6:

5.1 VACCINE DOSE

p.DOM-WT1-37: 1mg/dose/vaccine p.DOM-WT1-126: 1mg/dose/vaccine

5.2 VACCINE SCHEDULE

The DNA vaccine will be administered 6 times every 4 weeks followed by a further 6 vaccinations every 3 months to maximum of 24 months.

5.3 VACCINE ROUTE AND SITE

The vaccines will be injected by deep intramuscular injection (IM) followed by electroporation (EP) by a trained health care professional. The vaccines will not be mixed but will be administered into separate sites.

Refer to Section 6.4 for vaccine administration details.

5.4 DOSE MODIFICATIONS, REDUCTIONS AND DOSE DELAYS

There will be no dose reductions or dose modifications.

Haematological toxicity – If patients experience CTC toxicity >2, vaccination will not be administered. Further vaccination may be offered after normalization if appropriate in the opinion of the treating clinician and only after documented discussion with the UoSCTU and lead investigators. Severe local toxicity (CTC 3 or greater) at the site of injection, development of clinically relevant anti-DNA antibodies or rheumatoid factors, clinical or biochemical evidence of muscle destruction (CTC 3 or greater) or other unexpected toxicity will lead to termination of the vaccination of that patient.

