7.1.8 OTHER SYSTEMIC TOXICITY

Haematological toxicity: It is possible that vaccination with WT1 may cause cytopaenias in patients who have a hypocellular low marrow reserve (hypocellular bone marrow). This is because WT1 is also expressed at low levels in normal CD34+ stem cells. To minimise the possibility of this, we will exclude patients with low marrow reserve (bone marrow cellularity <20%). Patients who develop cytopaenia will be treated with 5 days of intravenous methylprednisone (1-2 mg/kg). This steroid treatment will not start for 2-3 weeks after the start of cytopaenia to allow time to determine if cell counts rebound. They will also be given supportive care including blood products, growth factors and antibiotics as clinically indicated until the counts recover. The development of other systemic toxicity appears unlikely. FBC, biochemistry, in particular renal function and clinical AE will be assessed by CTC criteria.

• If CTC toxicity >2 occurs in a particular patient, vaccination will be paused. Further vaccination may be offered after normalization if appropriate in the opinion of the treating clinician and only after documented discussion with the UoSCTU and lead investigators.

Cardiac or renal toxicity: It is possible but from the available dataset in the literature unlikely, that the patients may develop immune related toxicity that affects the kidney or cardiac function. Patients will therefore have regular monitoring of their renal function, including urine sampling for proteinuria, and an ECG before any vaccination dose is given. Additional tests will be undertaken as clinically indicated, should signs of renal or cardiac dysfunction occur.

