8.2 CAUSALITY

Most adverse events and adverse drug reactions that occur in this trial, whether they are serious or not, will be expected treatment-related toxicities due to the drugs used in this trial. The assignment of the causality should be made by the investigator responsible for the care of the subject using the definitions in the table below.

If any doubt about the causality exists the local investigator should inform the University of Southampton Clinical Trials Unit (UoSCTU) who will notify the Chief Investigator. Pharmaceutical companies and/or other clinicians may be asked for advice in these cases.

In the case of discrepant views on causality between the investigator and others, all parties will discuss the case. In the event that no agreement is made, the MHRA will be informed of both points of view.

Relationship	Description
Unrelated	There is no evidence of any causal relationship
Unlikely	There is little evidence to suggest there is a causal relationship (e.g. the event did not occur within a reasonable time after administration of the trial medication). There is another reasonable explanation for the event (e.g. the subject's clinical condition, other concomitant treatment).
Possible	There is some evidence to suggest a causal relationship (e.g. because the event occurs within a reasonable time after administration of the trial medication). However, the influence of other factors may have contributed to the event (e.g. the subject's clinical condition, other concomitant treatments).
Probable	There is evidence to suggest a causal relationship and the influence of other factors is unlikely.
Definitely	There is clear evidence to suggest a causal relationship and other possible contributing factors can be ruled out.

8.3 **REPORTING PROCEDURES**

All adverse events should be reported. Depending on the nature of the event the reporting procedures below should be followed. Any questions concerning adverse event reporting should be directed to the UoSCTU in the first instance. A flowchart will be provided to aid in the reporting procedures.

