10.2 ANALYSIS PLAN

Molecular Analysis

The analyses on molecular response will be performed on all patients with molecular data at a minimum of 2 post-baseline time points (HLA A2 positive patients must also have received at least 1 dose of the vaccine).

Immunological Analysis

To be evaluable for immunological response, positive HLA A2 patients must receive at least 1 dose of the vaccine and the immunological testing must be available until at least week 8 post first dose.

Safety Analysis

For safety analyses, all patients with positive HLA A2 status who received at least one study drug administration will be evaluable for toxicity. All controls will be included in the safety analyses, where relevant.

Other Analysis

For all other analyses, an intention to treat principle will be used.

10.2.1 ANALYSIS FOR CML PATIENTS ONLY:

Primary:

The primary endpoint is molecular response of BCR-ABL (major or minor response or CMR). For the purpose of analysis, response (as defined by section 9.6) will be measured at weeks 4, 8, 12, 16, 20, 32 and 11, 17 and 23 months. Fisher's exact test will be used to compare differences in proportions of molecular response in CML patients versus controls.

Secondary:

The primary analysis will be repeated for major response or CMR of BCR-ABL.

The analysis methods used for BCR-ABL will be repeated for WT1.

Progression free survival, duration of response and overall survival (as defined in Section 2.2) will be estimated using the method of Kaplan and Meier for each group. Survival estimates will be presented with 90% confidence intervals. These endpoints will also be compared between the CML patients and controls using log-rank tests.

Progression free survival for CML patients is defined in Section 2.2 and is measured as the time from date of consent to the study to date of progression or death from any cause. Alive patients who are progression free will be censored at their date of last follow up. Similar analysis will be performed for overall survival and duration of response.

Toxicity will be collected and evaluated according to the NCI CTC toxicity scale (v4.0) and compared between the vaccinated and control groups by Fisher's exact test.

10.2.2 ANALYSIS FOR AML PATIENTS ONLY:

Primary:

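### A possibly vaccine-related grade 3 toxicity must end vaccination under section 4.4, yet sections 5.4 and 7.1.8 allow restart with no causality condition

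*Protocol*

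**What the plan says.** Three sections of the Protocol act on the same kind of event.

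- **Section 4.4 (Withdrawal criteria)** lists circumstances in which study treatment is stopped. One reads: "Any patient who experiences a WHO CTC grade 3 adverse reaction (AR), possibly or likely to be related to vaccination will discontinue further vaccination". The bullet excepts no organ system.
- **Section 5.4 (Dose modifications, reductions and dose delays)** has a separate haematological rule. Above CTC grade 2 the vaccine is withheld, and then: "Further vaccination may be offered after normalization if appropriate in the opinion of the treating clinician and only after documented discussion with the UoSCTU" and the lead investigators. The section goes on to list toxicities that terminate vaccination, starting with: "Severe local toxicity (CTC 3 or greater) at the site of injection, development of clinically relevant anti-DNA antibodies or rheumatoid factors".
- **Section 7.1.8 (Other systemic toxicity)** opens its haematological paragraph with: "It is possible that vaccination with WT1 may cause cytopaenias". It describes rescue treatment for cytopaenia, mentions monitoring of blood counts, biochemistry, renal function and clinical events, and then gives a bullet: "If CTC toxicity >2 occurs in a particular patient, vaccination will be paused. Further vaccination may be offered after normalization", subject to the same clinician judgement and central discussion as 5.4.

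Causality is graded in section 8.2 on five levels: Unrelated, Unlikely, Possible, Probable and Definitely. The Possible level begins: "There is some evidence to suggest a causal relationship (e.g. because the event occurs within a reasonable time after administration of the trial medication". It allows that other factors, such as the patient's clinical condition, may have contributed.

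**The concern.** CTC toxicity above 2 includes grade 3. A grade 3 haematological reaction judged at least possibly related to vaccination therefore meets the trigger in 4.4 and the triggers in 5.4 and 7.1.8. The first ends vaccination. The other two leave re-challenge open once counts have normalised. Neither 5.4 nor 7.1.8 refers to 4.4 or mentions causality, and 4.4 refers to neither of them.

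What is at stake is re-exposure of a patient after a suspected reaction to the investigational product. Cytopaenia is also the haematological risk that 7.1.8 itself names. The overlap is not confined to proven vaccine effects: under 8.2, timing after a dose can support a classification of Possible, and that is enough to trigger 4.4.

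**Working it through.** The Protocol gives no figure on this point, so there is none to reproduce. The check sets the rules side by side and takes one type of event at a time. It reads the causality wording of 4.4 as covering the 8.2 classes Possible, Probable and Definitely.

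| Event | 4.4 | 5.4 | 7.1.8 | Result |
|---|---|---|---|---|
| Grade 3 haematological, Unrelated or Unlikely | Grade 3 bullet not triggered | Withhold, restart allowed | Pause, restart allowed | Consistent |
| Grade 3 haematological, Possible or higher | Discontinue | Withhold, restart allowed | Pause, restart allowed | **Conflict** |
| Grade 3 other systemic (e.g. renal), Possible or higher | Discontinue | Haematological rule does not apply | Pause, restart allowed | **Conflict** with 7.1.8 |
| Grade 3 other systemic, Unrelated or Unlikely | Grade 3 bullet not triggered | Haematological rule does not apply | Pause, restart allowed | Consistent; 7.1.8 is the explicit pause rule |
| Severe local toxicity or muscle destruction, grade 3 or greater | Terminate | Terminate | Not the subject of this section | Consistent |
| Grade 4 haematological, Possible or higher | Not named in the grade 3 bullet; falls to the general item on unacceptable toxicity | Withhold, restart allowed | Pause, restart allowed | Left open |

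Four observations follow.

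1. The conflict needs both a grade above 2 and a causality class of Possible or higher. Outside that cell the rules agree.
2. The 7.1.8 bullet is not worded as haematological. It sits under a heading on systemic toxicity and follows a sentence covering biochemistry, renal function and clinical events. Read literally, it extends the conflict to other systemic reactions.
3. The 4.4 bullet names grade 3 only. The more severe grade 4 reaction is thus covered less explicitly than grade 3.
4. Sections 4.5, 6.4.2, 7.1.2, 7.1.6, 8 and 12.1 were checked for a precedence clause, and none has one.

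Effect on the analyses: section 10.2 requires one vaccine dose and two post-baseline molecular time points for the molecular analysis. The immunological and safety analyses have their own dose-based rules. For the rest: "For all other analyses, an intention to treat principle will be used". Stopping vaccination does not by itself remove a patient from follow-up or from the intention-to-treat analyses.

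**The case against.** **Only stopping is mandatory.** Section 4.4 orders discontinuation, while restart in 5.4 and 7.1.8 is permitted and never required. A site that stops breaches nothing. This stands, and it limits the point. A reader might infer that the Protocol prescribes two actions that cannot both be obeyed. The documents do not support that, because one course satisfies every section. The fault is that one section permits what another forbids.

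**The rules can be applied in sequence:** hold above grade 2, assign causality, stop if related, otherwise consider restart. This is sensible and is what the fix below writes down. The Protocol does not state it, and 7.1.8 reaches its pause from a paragraph on cytopaenia that the vaccine may cause.

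**The specific rule may be meant to override the general one.** Section 5.4 sets out a haematological hold and then repeats the 4.4 terminations for other toxicities, which suggests separate handling. Section 7.1.8 also expects that counts may recover: "This steroid treatment will not start for 2-3 weeks after the start of cytopaenia to allow time to determine if cell counts rebound". A reader might infer that 5.4 governs. That is plausible, but no text says so, and 4.4 applies to any patient. A mandatory stopping rule should not be displaced by inference.

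**Restart is centrally controlled.** Each restart needs documented discussion with the trials unit and lead investigators. The Trial Management Group reviews event listings every 2 to 3 months, and the DMEC reviews safety (section 12.1). A reader might infer that sites would be left with no common rule. That goes too far, since every restart passes through one central route. The discussion concerns whether restart is appropriate, however, and does not settle whether 4.4 allows it.

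**The event may be rare.** Sections 1.7 to 1.9 report no significant haematological toxicity in the prostate electroporation study, no vaccine-related serious adverse events in more than 80 patients, and no marrow toxicity in the WT1 mouse model. Patients with marrow cellularity below 20% are excluded. The human data come from earlier constructs, so they do not establish a low rate here. They do argue against assuming a high one.

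**Conclusion.** Wrong as written. For a grade 3 reaction classed Possible or higher, section 4.4 rules out further vaccination, while 5.4 (haematological) and 7.1.8 (any systemic toxicity, on its wording) leave restart available. No precedence is stated.

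The size is limited. It is a conflict between safety rules, with a compliant and safe default and a central check before any restart. No frequency is claimed. A reader might be tempted to multiply an assumed rate by the planned number of vaccinated patients, but the Protocol gives no rate of related grade 3 haematological toxicity. The denominator is not settled either: section 10.1 gives 32 CML patients needed or 36 to be recruited, hence 32 + 39 = 71 or 36 + 39 = 75 with the AML group. Nor is there a basis for inferring a loss of power or a change in error rates, since stopped patients stay in the analyses described above.

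The conclusion rests on the plain reading that CTC above 2 includes grade 3, and that the causality wording in 4.4 includes the Possible class of 8.2.

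**What to change.** Keep section 4.4 as the governing rule and align the other two sections with it.

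- **4.4:** change the bullet from grade 3 to grade 3 or greater.
- **5.4:** limit restart after haematological toxicity above grade 2 to events classed Unrelated or Unlikely under section 8.2, and refer to 4.4 for all others.
- **7.1.8:** add the same limit and cross-reference. Leave the pause covering all systemic toxicity. Narrowing it to haematology would leave an unrelated grade 3 renal or other systemic event without an explicit pause rule.

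The reverse choice, exempting haematological reactions from 4.4, would also remove the contradiction. It would do so by giving up a mandatory stop after a suspected vaccine reaction, so it is not preferred.

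**Cost:** a short wording amendment to three sections, reviewed as section 11.3 requires. No extra patients, procedures or CRF fields are needed. The downside is that a patient whose cytopaenia is classed only as Possible, and may come from the disease or the tyrosine kinase inhibitor, loses further vaccination. That patient remains in follow-up and in the intention-to-treat analyses.
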